15.0 Background

In November 2020 – less than half-way through recruitment for the FAMS 2.0 RCT, we applied for a competing revision to NIH to support expanding the aims of the original R01 to include secondary data analyses from the FAMS 2.0 RCT and exit interviews.

Using cluster analysis with data from a large cohort of adults with T2DM, we identified 4 types of diabetes-specific family functioning. Type was independently associated with diabetes outcomes, including glycemic control (primary outcome of FAMS 2.0 RCT) and psychosocial wellbeing (diabetes distress and global well-being, secondary outcomes of FAMS 2.0 RCT). Because this evidence suggests effects of the FAMS 2.0 intervention may vary by type of diabetes-specific family functioning, we added the typology assessment measures to the RCT surveys. This addition will allow us to explore type as a moderator of intervention engagement and effects. The addition of exit interviews will help inform future intervention efforts by type.

The aims of the FAMS 2.0 RCT are unchanged.

16.0 Rationale and Specific Aims

Aim 1. Validate the diabetes-specific family functioning typology longitudinally in a diverse sample to:

- 1a.** Determine if similar types emerge in the more diverse RCT sample at baseline.
- 1b.** Examine type stability over time in the control group.
- 1c.** Examine associations between type and outcomes prospectively in the control group. Findings will enhance the utility of the typology in diverse samples and the clinical validity of the typology.

Aim 2. Explore diabetes-specific family functioning type as an effect modifier of FAMS 2.0. We will use mixed methods to understand how efficacy of the FAMS 2.0 intervention was moderated by baseline type.

- 2a.** Examine effect modification by type over the 15-month RCT and explore which components of the intervention were/were not engaging for each type.
- 2b.** Complete exit interviews with n=80 intervention participants using rolling purposive sampling to ensure representation of each type.

Upon completion of these aims, we will know how to identify patients for whom the FAMS 2.0 intervention will be maximally effective to inform future implementation efforts and we will have hypotheses about what intervention components may maximize effects for other patients in the future.

17.0 Study Procedures

Procedure/Activity	Frequency
Survey (patient participants)	Baseline, 6mo, 9mo, 15mo – same as for

	the FAMS 2.0 RCT
Exit Interviews	Upon completion of the study (15mo) participants assigned to intervention were invited to participate in an exit interview

Each patient participant survey for the FAMS 2.0 RCT included measures of the typology dimensions.

Measures of Dimensions for Typology	
For these items, respondents are asked to "think about the person who is most involved in your diabetes on a regular basis."	
Collaborative Coping (3 dimensions): Cognitive Compensation, Interpersonal Enjoyment, & Frequency	Perceptions of Collaboration Questionnaire (PCQ) assesses Cognitive Compensation (degree to which collaboration is needed to overcome cognitive deficits or decline; $\alpha=0.80$), Interpersonal Enjoyment (degree to which collaboration provides encouragement and closeness; $\alpha=0.64$), and Frequency of Collaboration ($\alpha=0.79$)
For these items, "think about the people closest to you in your everyday life - it doesn't matter if they live with you."	
Received support (2 dimensions): helpful & harmful	Family/Friend Involvement in Adults' Diabetes (FIAD) assesses the helpful and harmful aspects of received support for diabetes self-care activities in the past 30 days. 9-items assess helpful (e.g. "How often do your family members exercise with you or ask you to exercise with them?"; $\alpha=0.87$) and 7-items assess harmful (e.g. "How often do your family members bring foods around that you shouldn't be eating?"; $\alpha=0.72$). Harmful items query frequency of undermining/ sabotaging behaviors and nagging/arguing about self-care
Perceived support: Autonomy Support	Important Other Climate Questionnaire (IOCQ) assesses perception of the degree to which others support the individual's personal agency. We adapted the 6-item IOCQ to be specific to diabetes as the developers recommend and to reference more than one important other (e.g. "My important others try to understand how I see my diabetes before suggesting any changes"; $\alpha=0.89$)
Perceived support: Criticism	The criticism scale from the Family Emotional Involvement and Criticism Scale, adapted to be specific to diabetes (e.g. "My important others find fault with the things I do to manage my diabetes"; $\alpha=0.71$)
Match (2 dimensions): Effectiveness & Satisfaction	Single items: "How effective are your friends and family at dealing with troubles or issues related to your diabetes management?"; "How satisfied are you with your friends and family members' involvement in dealing with troubles or issues related to your diabetes management?"

Only patient participants assigned to the intervention are recruited for exit interviews.

FAMS 2.0 (PI: [name])

R01-DK119292

NCT04347291

Following the 15-month follow-up period, some intervention participants will be asked to participate in an exit interview to collect feedback about the intervention and learn about their experience. We will use baseline data from the RCT to purposively sample $n=80$ participants to complete interviews, such that $n=15-20$ represent each of the four typology types. Exit interviews are completed over the telephone, last ~30-45 minutes, and participants will provide verbal informed consent before any interview data is collected. Questions focus on (a) diabetes-specific family functioning prior to, during and after the intervention, (b) which intervention components they felt worked best/least for them, and (c) desirability and acceptability of alternative intervention formats and content.

Participants who complete an interview are compensated \$40. Interviews are audio recorded and transcribed for analysis.

18.0 Statistical Considerations

This analysis leverages the outcomes measures data already collected during the RCT, including: hemoglobin A1c, diabetes distress, global well-being, self-efficacy, self-care behaviors (dietary behavior, physical activity, medication adherence) and helpful and harmful family/friend involvement.

This analysis leverages engagement data already collected during the RCT, including: enrollment of a support person, text message response rates, coaching session completion rates, elements of coaching protocol including completing rates of goals set, completion of verbal contract to engage friends/family.

The FAMS 2.0 RCT was not designed to test effect modification or moderation by type. Tests of effect modification are exploratory and intended for hypothesis generation, therefore we will interpret patterns of effects and use $p < .10$ as our threshold to discern potentially meaningful differences in intervention effects.

19.0 Privacy/Confidentiality Issues

Informed consent for patient participant exit interviews is obtained verbally over the phone before completing the exit interview. Exit interviews are recorded following participants' consent and the audio files and transcripts are stored using the subject's unique ID on a secure VUMC server. The transcripts are de-identified and will be stored separately from other participant data for at least ten years after the close of the study. Recorded exit interviews will be stored separately, on a secure VUMC until the close of the study, at which point they will be destroyed.

**Version date 11/20/2023**

## Statistical Analysis Plan for NCT04347291

Our conceptual framework is shown in **Figure 1**. Outcomes include patient participants' HbA1c (primary), diabetes distress and well-being (secondary). Our intervention targets include three hypothesized mediators for patient participants: improved diabetes self-efficacy, improved diabetes self-care behaviors (i.e., dietary behavior, physical activity, and medication adherence), and improved diabetes-specific involvement from family and friends (i.e., increased helpful involvement and reduced harmful involvement). Potential moderators of patient participants' effects are gender, minority race/ethnicity, socioeconomic disadvantage, and support person cohabitation.

Primary support person outcomes are support burden and diabetes distress. Our intervention targets/hypothesized mediators for support persons are self-report on diabetes-specific support provided to the patient participant (i.e., increased involvement, increased helpful involvement and reduced harmful involvement). Exploratory analyses test if improvements in support person outcomes are mediated by improvements in patient participant outcomes (i.e., HbA1c, diabetes distress, well-being). Support person gender and cohabitation are potential moderators of support person effects.

**Figure 1. Conceptual Framework.** FAMS 2.0, Family/friend Activation to Motivate Self-Care version 2.0 evaluated in this study.

Intention-to-treat principles will be used to analyze all available data with two primary models: repeated measures regression models (generalized estimating equations; GEE) to assess main effects and subgroup effects, and structural equation modeling (SEM) techniques to test mediation. To address missing data, we use multiple imputation via chained equations with a total of M=500 iterations. One imputation model includes baseline, 6- and 9-month data during the intervention and a second imputation model includes baseline and 12- and 15-month data for sustained effects.

To estimate FAMS' main effects and subgroup effects, we will use generalized estimating equations (GEE) with a working-independence correlation structure and identity link. Models will be adjusted for insulin use at baseline and baseline value of the outcome of interest (via a restricted cubic spline with three knots) for each model. We will allow a two-way interaction between time and condition and a two-way spline interaction between time and baseline value of the outcome. Differences between arms will be tested based on a linear combination of regression coefficients at each time point (based on Wald-based test with one degree of freedom). Point estimates and corresponding 95% confidence intervals will be obtained for each follow-up time point, to graphically display trajectories in adjusted mean outcomes difference over 15 months. We will explore subgroups effects (i.e., divided sample) to determine for whom the intervention was most or least effective using the same models as described above.

For each intervention target (**Figure 1**), we fit models as described above. Continuous measures were analyzed using the GEE model. The summative one-item physical activity measure was ordinal, and therefore analyzed using an ordinal regression model (odds ratios obtained on cumulative logit/proportional odds scale). Each model was run three times, to

estimate during (6-months), post (9-months) and sustained (15-months) intervention effects.

For mediation analyses, we model between-subjects mediation with path analysis with an SEM framework as suggested in **Figure 1**, including multiple mediators. Mediation models include intervention targets at both 6 and 9 months as mediators and a single outcome (i.e., HbA1c, diabetes distress or well-being). We ran this model separately for each outcome at 9, 12 (H1cA1c only) and 15 months. For parsimony, we restricted the number of mediators guided by findings evaluating intervention effects on these mediators, opting for continuous and sensitive mediator measure(s) of self-care behaviors unless both measures were significantly improved by the intervention. We used Amos version 29 regression imputation function to address missing data, running each imputation separately for each model.

Path coefficients and indirect effects evaluate mediation using 2,000 bootstrap samples for bias-corrected estimates and 95% confidence intervals for effects. Paths from condition to mediators will determine if FAMS 2.0 improved each mediator relative to control, and indirect effects will identify mechanisms by which FAMS 2.0 affected outcomes. In addition to examining mediators of patient participants' outcomes, we examine dyadic mediation by assessing whether support person outcome changes are explained by change in their own involvement and/or by improvements in the patient participants' outcomes (e.g., mediator: change in patient participant HbA1c, outcome: change in support person well-being).

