5.0 Study Procedures

Procedure/Activity	Frequency
Survey (patient participants and SPs)	Baseline, 6mo, 9mo, 15mo
A1c test (patient participants)	Baseline, 6mo, 9mo, 12mo, 15mo
Diabetes educational materials (patient participants and SPs)	Baseline and quarterly (4x per year)
FAMS 2.0 mobile phone intervention (patient participants)	Approx. 2 texts per day for 9 months
FAMS 2.0 mobile phone intervention (SPs)	Approx. 4-5 texts per week for 9 months
FAMS 2.0 phone coaching (patient participants)	Approx. 25-30 min. calls once a month for nine months

All data were stored in REDCap. Information collected as part of regular care was collected from patient participants' EMR (e.g., birthdate, gender, A1c test results, height, weight, BMI, medications, co-morbidities, etc.). Surveys were administered to all participants at baseline, 6, 9, and 15 months—online, mailed copy, or by telephone. A1c results were collected from persons with diabetes with each survey as well as at 12 months. Participants received mail-in HbA1c test kits provided by CoreMedica Laboratories. HbA1c values collected as part of clinical care were also extracted from the EMR.

Patient participants assigned to control group:

Text messages - Patient participants received a text message when their A1c result was ready (baseline, 6mo, 9mo, 12mo, 15mo).

Patient/SP dyads assigned to FAMS intervention:

Phone coaching - Patient participants completed a phone coaching session with a trained coach once a month for nine months (10 total sessions; 9 core sessions and a brief 10th wrap-up session). Coaching sessions lasted 25-30 minutes each. Coaching sessions included:

- Setting a behavioral goal that can be completed at least 4 days per week in the categories of dietary behavior, physical activity, or stress management (setting and/or adjusting the goal, check in on goal progress)
- Skill building around family/friend involvement in diabetes management, specific to the goal (discussion of helpful and/or harmful family involvement, coach-selected skill building to align with and address the patient participant's experiences, setting a verbal contract to practice the learnt skill with a specific identified person and – at subsequent sessions – check in on how that went).

FAMS 2.0 (PI: [name])

R01-DK119292

NCT04347291

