7.0 Study Withdrawal/Discontinuation

During the enrollment phase, persons with diabetes who did not return their baseline survey after 5 weeks and were unresponsive to research staff communication were administratively withdrawn. If persons with diabetes were not reached for their condition assignment call within one month, then they and their support person (if applicable) were administratively withdrawn.

If a participant expressed wishes to withdrawal from the study, study staff would contact the participant. Study staff followed a protocol to determine which levels of participation the patient does/does not want:

- (1) limited intervention (e.g., no text messages but willing to complete coaching if so assigned) but will complete study assessments
- (2) no intervention (opt out of all assigned study components) but will complete study assessments
- (3) no surveys but okay with completing A1c kits or vice versa and receiving assigned components
- (4) no surveys nor A1c tests but will allow study staff to review and extract relevant data to the study from their EMR
- (5) no further participation

If a SP expressed that they did not want to participate in the study, study staff followed a protocol to determine what level of participation they do/do not want:

- (1) limited intervention – no text messages but will complete study assessments
- (2) no surveys but okay with receiving text messages
- (3) no further participation

Patients can still engage with all aspects of the study if their SPs withdraws. If the patient withdraws to the level of no further participation, their SP would be administratively withdrawn. If a SP withdraws to the level of no further participation, we would contact their patient partner to let them know their SP has withdrawn completely from the study. If a support person withdraws for any reason, the patient participant could identify another support person to participate in the study with them.

If a participant expressed wishes to withdrawal and could not be reached by study staff to confirm their level of withdrawal, the participant was treated as a full withdrawal with no further participation (option 5 from the list above.)

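### The SAP names no engagement variable for its imputation models, although coaching and text engagement were recorded; if FAMS patients who disengage are lost more often, the A1c effect may lean modestly toward FAMS

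*SAP*

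**What the plan says.** The SAP sets out its principle as "Intention-to-treat principles will be used to analyze all available data". On missing data it says "To address missing data, we use multiple imputation via chained equations with a total of M=500 iterations", and then "One imputation model includes baseline, 6- and 9-month data during the intervention and a second imputation model includes baseline and 12- and 15-month data". Nothing further is given about the imputation: no variable list, no statement on arm, no auxiliary variables. The main analysis is GEE with a working-independence correlation structure, adjusted for baseline insulin use and the baseline value of the outcome. No sensitivity analysis for outcomes missing not at random is described.

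Engagement measures appear in Protocol section 18.0, for the added typology work: "This analysis leverages engagement data already collected during the RCT, including: enrollment of a support person, text message response rates, coaching session completion rates". They are given no role in the main analysis.

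Protocol section 7.0 lets patients stop the intervention and stay under assessment. One level is "no intervention (opt out of all assigned study components) but will complete study assessments"; another is "no surveys nor A1c tests but will allow study staff to review and extract relevant data to the study from their EMR". Section 5.0 adds that "HbA1c values collected as part of clinical care were also extracted from the EMR". A patient who asks to withdraw and cannot be reached is treated as having left entirely, and that level does not mention record extraction.

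**The concern.** Working-independence GEE does not borrow information across a patient's visits, so protection against informative loss rests on what the imputation model contains. Only FAMS patients have coaching and near-daily texts to stop. In that arm, engagement plausibly predicts both whether a later A1c is obtained and how much benefit remains. That is the usual reason to include a variable as an auxiliary.

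Without it, a lost FAMS patient is imputed from the observed FAMS patients with similar earlier values. If continuers are over-represented among those observed, the imputed A1c is too favourable. An intention-to-treat estimate should carry the outcome the patient had after stopping. At stake is a small one-sided error in the primary outcome.

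The exposure is greatest in two places. A patient lost before 6 months has no on-treatment A1c to show that benefit was lost. The second imputation model lists no 6- or 9-month data, so the 12- and 15-month estimates lack that partial correction for everyone.

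**Working it through.** **The plan's own figures (Protocol section 8.0).** Difference 0.5, SD 1.5, 80% power, 5% level taken as two-sided.

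- Per arm: n = 2 × 1.5² × (1.96 + 0.8416)² / 0.5² = 141.3, so 142, or 284 in all. Power at 142 per arm is 80.2%.
- Enrolment: 284 / 0.85 = 334.1, against 334 stated. The figures reproduce.
- Standard error of the difference: 1.5 × √(2/142) = 0.178.

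**Assumptions not in the documents.** The effect is 0.5 while engaged. A share p of FAMS patients stop and lose the whole effect. Stoppers are lost with probability s and continuers with probability c. Imputation is within arm.

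**Formula for imputation from baseline A1c only.**

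- True intention-to-treat effect = 0.5 × (1 − p).
- Expected estimate = 0.5 × (1 − p)(1 − c) / [(1 − p)(1 − c) + p(1 − s)].

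Example, p = 0.25, s = 0.45, c = 0.05. Loss is 0.25 × 0.45 + 0.75 × 0.05 = 0.15. The true effect is 0.375. The estimate is 0.5 × 0.7125 / (0.7125 + 0.1375) = 0.419. The overstatement is 0.044.

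**Simulation.** 400,000 patients per arm, about 15% loss in each arm, correlation 0.6 between baseline and 6-month A1c, 6-month A1c observed for everyone. Entries are overstatement in A1c points.

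| p | s | c | Baseline only (formula) | Baseline only (simulated) | Baseline + 6 months | Baseline + engagement indicator |
|---|---|---|---|---|---|---|
| 0.15 | 0.50 | 0.088 | 0.031 | 0.030 | 0.011 | about 0 |
| 0.25 | 0.45 | 0.05 | 0.044 | 0.044 | 0.017 | about 0 |
| 0.25 | 0.60 | 0 | 0.066 | 0.064 | 0.024 | about 0 |
| 0.30 | 0.50 | 0 | 0.062 | 0.062 | 0.024 | 0 |
| 0.25 | 0.15 | 0.15 | 0 | about 0 | about 0 | about 0 |
| 0.15 | nearly 1 | 0 | 0.075 | 0.076 | 0.030 | not repaired |

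The baseline-only columns correspond to a patient with no 6-month value, or to the second model as listed. The baseline + 6 months column corresponds to the first model for a patient who gave a 6-month A1c.

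**Worst case.** Every lost FAMS patient had stopped, kept none of the effect, and is imputed as a continuer. The overstatement is 0.5 × loss: 0.05, 0.075 and 0.10 at 10%, 15% and 20% loss. If half of the lost had stopped, or all had but kept half the effect, these halve to 0.025, 0.0375 and 0.05. In the last table row almost no stopper is observed, so an engagement coefficient cannot be estimated.

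**At trial size.** With 167 FAMS patients (334 / 2), 15% loss tied to engagement, and most of the lost also missing 6-month A1c, the bias toward FAMS was about 0.015 to 0.05 without engagement and about 0 with it. The standard deviation of the estimate rose by only a few per cent, and its root mean squared error was equal or lower.

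**The case against.** The strongest objection is that a list of time points is not a list of variables. A reader might infer that the SAP excludes engagement, but it states no such exclusion; it is silent on every imputation variable, arm included. That stands, and the point is therefore that engagement is not named.

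A reader might also infer that lost FAMS patients are imputed as if still engaged. The documents do not support that. The withdrawal levels keep some stoppers in assessments, record extraction offers a further route to A1c, observed stoppers contribute to the FAMS imputation, and 6-month A1c carries part of the effect of stopping.

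Nor is a favourable bias established as fact. It needs arm in the imputation model, heavier loss among stoppers, and loss of benefit after stopping. If arm were left out, imputed values would pull toward no difference. With equal loss the bias is zero.

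The size is small. If benefit is graded with engagement, baseline-only imputation overstates a 0.50 effect by about 0.02 to 0.03, and adding 6-month A1c reduces this to about 0.004 to 0.012. Even 0.06 is about a third of a standard error (0.06 / 0.178 = 0.34).

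The last objection is that a stopped-intervention indicator might be unstable with few observed stoppers. The assumed rates leave about 167 × 0.15 × 0.50 = 13 to 167 × 0.25 × 0.55 = 23 of them in the first two table rows, and the trial-size check showed little loss of precision. The objection holds only when nearly all stoppers are unobserved.

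**Conclusion.** The point holds as a modest, conditional weakness in the imputation plan. With arm in the model, heavier loss among disengaged FAMS patients, and benefit lost after stopping, the A1c effect is overstated by roughly 0.01 to 0.06 points at 15% loss. The lower part of that range applies where 6-month A1c is available and used, and the upper part where it is not. The overstatement is zero if loss is unrelated to engagement. The ceiling at 15% loss is 0.075, or 0.42 of a standard error. Stop rates, loss by engagement, retained benefit and A1c correlations are all assumptions.

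A reader might take the ceiling as the expected error: 0.50 reported against 0.425, or 18% too large. That would be wrong, since it requires every lost FAMS patient to have stopped with no benefit kept and no observed stoppers to learn from. It supports a sensitivity analysis, not a claim about what auxiliary variables would gain.

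**What to change.** Amend the missing-data text of the SAP as follows:

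1. List the variables in each imputation model and impute separately by arm. This also preserves the planned time-by-condition interaction, and it is the natural way to use measures that exist only for FAMS patients.
2. In the FAMS arm, add the share of coaching sessions completed and the text response rate as auxiliary variables in both models. Add an indicator of having stopped the intervention if enough stoppers have observed outcomes.
3. Carry the 6- and 9-month data into the model for 12 and 15 months.
4. Add one delta-adjusted or reference-based sensitivity analysis for A1c, to cover the case where nearly all stoppers are unobserved.

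The cost is SAP wording and a rerun of the imputation on data already held. Intervals may be slightly wider and the effect estimate may be smaller.

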2.0 Rationale and Specific Aims

We built upon these promising initial findings by expanding and improving FAMS through usability testing and before evaluating FAMS 2.0 in a larger, 15-month randomized control trial (RCT) including support persons (SPs) in both the intervention and control condition. This project's focus aligns closely with the American Diabetes Association's new psychosocial standards and represents an advance in the use of technology to deliver patient and family-centered care. Moreover, this work has the potential to improve the social contexts in which adults live with T2D, key diabetes-related psychosocial outcomes for patients and their family/friends, and glycemic management.

FAMS 2.0 (PI: [name])
R01-DK119292
NCT04347291

The aims of this RCT are:

1. Among patient participants, to evaluate the effects of the expanded FAMS 2.0 intervention versus enhanced treatment as usual (print materials on T2D self-care and access to A1c results) on glycemic management (A1c; primary outcome) and psychosocial well-being (diabetes distress and global well-being; secondary outcomes). We examine effects during the 9-month intervention period and sustained effects after the intervention periods ends.
2. Among support person participants, to explore effects of the expanded FAMS 2.0 intervention versus enhanced treatment as usual (print materials) on psychosocial well-being (diabetes distress) and support burden.
3. To examine intervention effects on intervention targets including:
 - a. Patient participants: family/friend helpful involvement, family/friend harmful involvement, diabetes self-efficacy, and diabetes self-care behaviors
 - b. Support person participants: support person's own involvement in the self-management of the person with diabetes
4. To test hypothesized mediators and explore subgroups difference of intervention effects.

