8.0 Statistical Considerations

Power estimates were conservatively calculated based on a two-sample unequal variance *t*-test of 9-month A1c for a minimum detectable difference of 0.5%; we targeted enrollment of 334 dyads to obtain sufficient effective sample size to detect this effect. Allowing for a dropout rate of ~15%, an effective sample size of 284 (~142 per condition) provides 80% power to detect this minimum difference at a 5% significance

FAMS 2.0 (PI: [name])

R01-DK119292

NCT04347291

level assuming a standard deviation of 1.5%. For secondary outcomes and mediators, assuming skewness similar to A1c (in general it will be less) and retention of 80–90%, we will be able to detect standardized effect sizes of 0.32–0.34. Estimates of detectable effect were made via 40,000 simulations with a Beta distribution calibrated to approximate skewness similar to that observed in our prior work.

Our power will be greater than estimates, given our plans to use data imputation methods for missing data, and adjust for baseline values of the outcome(s) of interest and other covariates as needed per analysis, which should increase power by reducing the effective standard deviation of the outcome.

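### The imputation model for sustained effects leaves out the 6- and 9-month values already collected, which matters most for 15-month distress and well-being

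*SAP*

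**What the plan says.** The missing-data paragraph of the SAP (after Figure 1) plans "multiple imputation via chained equations with a total of M=500 iterations", divided between two models. For the intervention period, "One imputation model includes baseline, 6- and 9-month data during the intervention". For the later period, "a second imputation model includes baseline and 12- and 15-month data for sustained effects". No reason is given for the split, and no missing-data sensitivity analysis is described.

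The main analysis is "generalized estimating equations (GEE) with a working-independence correlation structure and identity link", adjusted for baseline insulin use and the baseline value of the outcome.

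On data collection, Protocol 5.0 states: "Surveys were administered to all participants at baseline, 6, 9, and 15 months". It then adds: "A1c results were collected from persons with diabetes with each survey as well as at 12 months". A1c values from routine care are also taken from the medical record.

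The later period belongs to Aim 1 (Protocol 2.0): "We examine effects during the 9-month intervention period and sustained effects after the intervention periods ends". That aim covers A1c, diabetes distress and global well-being.

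**The concern.** For a participant who completes month 9 and then drops out, the 6- and 9-month values say most about the missing 15-month value. The second imputation model, as described, does not use them. A GEE with working independence does not borrow across visits either, so imputation is the only route by which they could inform the 15-month contrast.

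The plan therefore relies on data being missing at random given baseline (plus the 12-month value for A1c), rather than given the whole observed history. That is stronger in the usual sense: loss after month 9 may not depend on how the participant was doing at month 9, beyond what baseline and any 12-month value explain. If it does depend on that, and differently in the two arms, the 15-month contrast is biased even though the values that would correct it are in the database.

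Survey outcomes are the most exposed, because nothing is surveyed at month 12. Protocol 7.0 also foresees participants who stop surveys but continue A1c kits or allow record extraction, so loss of survey data alone is to be expected.

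**Working it through.** **1. The plan's own figures.** Protocol 8.0 assumes a difference of 0.5, SD 1.5, 5% significance (taken as two-sided) and 80% power.
- Per arm: n = 2 × (1.960 + 0.842)² × 1.5² / 0.5² = 141.3, so 142, or 284 in all.
- Enrolment: 334 × 0.85 = 283.9.
- Secondary outcomes: the plan states "retention of 80–90%, we will be able to detect standardized effect sizes of 0.32–0.34". Detectable effect = 2.802 × √(2/n per arm). At 90% retention n = 150.3 and the result is 0.323 SD; at 80%, n = 133.6 and it is 0.343 SD.

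These reproduce. The concern is not an arithmetic error, and 0.33 SD is a fair yardstick for the survey outcomes.

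**2. What each sustained contrast has available**

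| Outcome at 15 months | Collected at | Own values listed in the second model | Own values left out |
|---|---|---|---|
| Distress, well-being | 0, 6, 9, 15 | 0, 15 | 6, 9 |
| A1c | 0, 6, 9, 12, 15 | 0, 12, 15 | 6, 9 |

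**3. Size of the bias: survey outcomes.** From the documents: N = 334, 1:1 allocation, 80–90% retention, an effect of about 0.33 SD. Assumed, because the documents do not give them: correlation 0.6 with baseline and 0.65–0.75 between follow-ups; late loss with odds ratio 2 per SD of the 9-month value; early loss random, with months 6 and 9 missing as well. There were 3,000 simulated trials per scenario. The 15-month value was imputed from baseline and arm, then from those plus months 6 and 9, and analysed by a baseline-adjusted arm contrast.

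Bias in SD units without the 6- and 9-month values:

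| Dependence of late loss on the 9-month value | Timing of loss | 10% lost | 15% lost | 20% lost |
|---|---|---|---|---|
| One arm only | all after month 9 | 0.022 | 0.034 | 0.043 |
| One arm only | half earlier | 0.011 | 0.019 | 0.025 |
| Opposite by arm | all after month 9 | 0.045 | 0.069 | 0.088 |
| Opposite by arm | half earlier | 0.024 | 0.037 | 0.050 |

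Against 0.33 SD, the all-late rows are 7–13% and 14–27% of the effect. With the same dependence in both arms and 15% loss, the bias is at most 0.006 SD. The sign depends on which arm loses the worse-off participants.

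A separate large-sample calculation (600,000 subjects per scenario, correlations 0.5–0.6 with baseline and 0.6–0.8 between follow-ups, log-odds 0.7 per SD, all loss late, 15% lost) gave 0.034–0.044 SD for one arm, 0.067–0.090 SD for opposite arms and about zero for equal dependence. Adding months 6 and 9 reduced the bias to 0.002 SD or less.

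**4. A1c** (SD 1.5, assumed true effect −0.30, 15% lost, same odds ratio). Estimates without months 6 and 9:

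| Scenario | One arm | Opposite by arm |
|---|---|---|
| No 12-month A1c among those lost | −0.249 | −0.195 |
| All loss late, half with a 12-month A1c | −0.271 | −0.238 |
| Half lost early; half of late losses with a 12-month A1c | −0.282 | −0.262 |

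The bias runs from about 0.10 at worst to 0.02–0.04 in the last row, against a standard error of about 0.14. With months 6 and 9 added, the estimates are −0.298 to −0.302.

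**5. Precision.** The variance of the contrast is proportional to (1 − r₀²)/(1 − m) with baseline only, and to (1 − R²)/(1 − m) + (R² − r₀²) with all visits. Here m is the proportion lost, r₀ the correlation with baseline, and R² the variance explained by baseline and months 6 and 9. For r₀ = 0.6, correlation 0.7 between follow-ups and m = 0.15, R² = 0.596. The terms are 0.64/0.85 = 0.753 and 0.404/0.85 + 0.236 = 0.711, so the standard error falls by 1 − √(0.711/0.753) = 2.8%. Over the assumed correlations and 10–20% loss the fall is 1.5–5.8%. In the trial-sized simulations, where some scenarios had early loss, the standard error without the extra values was 0–3% larger.

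**The case against.** The best counter-argument is that the risk is conditional and usually small. Bias needs loss that depends on 9-month values differently by arm, and the documents show no such pattern. An odds ratio of 2 is one choice. At 15% loss with one-arm dependence, an odds ratio of 1.25 gives 0.013 SD (0.005 if half the loss is early) and 1.5 gives 0.020 SD (0.011). With 142 per arm and r = 0.6, the standard error is √(0.64 × 2/142) = 0.095 SD. The one-arm bias of 0.019–0.034 SD is then 0.20–0.36 standard errors, and 95% interval coverage stays near 93.5–94.5%. Only the opposite-by-arm, all-late case is plainly material: 0.069 SD, coverage about 89%. This stands, and it limits how serious the point is.

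Other objections hold in part:
- The two missing-at-random assumptions are not strictly nested, so stronger is used here in its practical sense.
- That the added values remove the bias follows from how loss was generated. They would not correct for loss that depends on unobserved later values.
- The SAP does not list every imputation variable. The second model may hold other predictors, such as 12-month A1c, that help a little with survey scores.
- The SAP is dated 11/20/2023 and describes some model fitting in the past tense, so a change now may come after results were seen.

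None of this gives a reason for leaving out the nearest available measurements of the same outcome.

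**Conclusion.** The concern holds. As written, the second imputation model omits the best available predictors of a missing 15-month value, and the GEE does not make up for it. For distress and well-being at 15% loss and an odds ratio of 2, the resulting bias ranges from negligible (same dependence in both arms) through 0.019–0.034 SD (one arm) to 0.037–0.069 SD (opposite arms). For A1c it is about 0.02–0.04 in the less extreme scenario and 0.05–0.10 near the worst case. The precision cost is a few percent of the standard error.

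These sizes rest on assumed correlations, odds ratio and timing of loss; the documents support only the sample size and overall retention. The 6- and 9-month contrasts, including the 9-month A1c comparison on which the trial is powered, use the first model and are untouched. The mediation analyses use a separate Amos imputation and are also outside this point. It should be fixed because the remedy is cheap, not because bias has been shown.

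**What to change.** Replace the two models with one chained-equations model (M = 500) containing condition and the baseline, 6-, 9-, 12- and 15-month data. At minimum, add each outcome's own 6- and 9-month values to the second model. If those values were in fact used, one sentence in the SAP saying so settles the matter.

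The cost is a change of SAP wording and a re-run of the 12- and 15-month analyses, with no new data. The imputation model becomes larger; if it does not converge, limit the additions to the same outcome's 6- and 9-month values. If sustained-effect results have already been seen, date and label the change and report the estimates from both imputation models side by side. A table of loss after month 9 by arm and 9-month value would show whether the conditions for bias are present.
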